6.2.3 Screen Failures

Participants who are consented to participate in the clinical trial, but who do not meet one or more criteria required for participation in the trial during the screening procedures, are considered screen failures. Screen failures will be immediately discontinued from the trial and will not receive CTR-US within the trial. Participants who are discontinued from the study due to screen failure may not be reconsidered for study enrollment at a later date. Study sites will document screen failures by recording the date of screening, an anonymized patient identifier, and the primary inclusion and/or exclusion criterion failure that resulted in the decision to discontinue the patient from the study.

6.2.4 Timing of Patient Screening

All baseline testing and evaluations should be performed as close to the time of the procedure as possible. If the subject's procedure date is more than 30 days from the baseline electronic patient reported outcomes completion, validated questionnaires must be repeated to ensure accuracy of baseline condition at the time of procedure.

7. SUBJECT ENROLLMENT

Subjects meeting all study inclusion/exclusion criteria after their screening evaluation will receive CTR-US. Only subjects who receive CTR-US will be considered enrolled in the study. If a subject has a CTR with a method other than CTR-US they will not be considered enrolled in the study. Eligible patients who do not receive treatment will be discontinued from the trial.

7.1 **PROCEDURE**

The key procedural steps involved in CTR-US are listed below.

- 1. Using real-time US visualization, identify relevant anatomical structures within the carpal tunnel.
- 2. Dissect synovial tissue from the undersurface of the TCL.
- 3. Insert the device through a small wrist incision and advance into the carpal tunnel.
- 4. Position the tip of the device distal to the distal TCL so that the TCL Blade will engage the distal TCL.
- 5. Confirm the position of the device under ultrasound, including the safety of surrounding structures.
- 6. Activate the Stealth MicroGuard balloons to create space within the carpal tunnel.
- 7. Deploy the TCL Blade by moving the slide button proximally to transect the TCL from distal to proximal until the TCL Blade passes into its proximal recessed position.
- 8. With the device or an elevator, probe the TCL to ensure a complete release.

Complete procedural details are provided in the Instructions for Use (https://sonexhealth.com/physicians/ultraguidectr/instructions-for-use).

Patients may undergo unilateral or simultaneous bilateral CTR-US procedures in this trial. The decision of which procedure to undergo will be made based on the clinical diagnosis and by shared decision-making between the patient and physician.

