9. ADVERSE EVENTS

An Adverse Event (AE) is defined as any adverse change (i.e., de novo or preexisting condition) from the subject's baseline medical condition occurring after the initial procedural incision has been initiated. Any AE which resolved and then recurred will be reported as a separate AE. A pre-specified listing of AEs will be documented on the Adverse Event eCRF.

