9.4 DEVICE FAILURES, MALFUNCTIONS AND NEAR INCIDENTS

Device failures or malfunctions will be reported to Sonex Health by the clinical sites. If the failure or malfunction results in an AE, the event shall be reported to the Sponsor within two (2) working days after the Investigator becomes aware of the event and reported to the IRB (if required) within the IRB required timeframe. The device involved in the incident should be returned to the Sponsor for evaluation.

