10.2 ANALYSIS POPULATIONS

The primary statistical analyses will be performed on subjects who meet all study eligibility criteria and receive treatment with CTR-US. Subjects who withdraw from the study prior to treatment will not be included in the analysis.

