10.2.1 Duration Variables

Study day 0 is the day the subject receives office-based CTR-US. Postoperative study day will be calculated relative to day 0 as follows:

Study Day = (Date of Event – Date of Treatment)

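### As worded, section 7 leaves a CTR-US attempt converted after incision (and arguably an abandoned one) with no defined population, AE denominator or required follow-up

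*Combined protocol and SAP*

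**What the plan says.** Section 7 (Subject Enrollment) has three rules that depend on what the subject finally received:

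- Enrolment requires the study procedure itself: "Only subjects who receive CTR-US will be considered enrolled in the study".
- Release by another technique takes the subject out: "If a subject has a CTR with a method other than CTR-US they will not be considered enrolled in the study".
- Going untreated ends participation: "Eligible patients who do not receive treatment will be discontinued from the trial".

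Section 10.2 gives the only analysis population: "The primary statistical analyses will be performed on subjects who meet all study eligibility criteria and receive treatment with CTR-US". On early withdrawals the same section adds: "Subjects who withdraw from the study prior to treatment will not be included in the analysis". Section 10.2.1 sets the time origin in the same terms: "Study day 0 is the day the subject receives office-based CTR-US". The related-AE endpoint in section 8.2.7 covers 90 days from treatment, and section 10.2.3 calculates AE incidence per subject.

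The safety sections start elsewhere. Section 9 defines an AE as an adverse change "occurring after the initial procedural incision has been initiated". Section 9.4 foresees device problems: "Device failures or malfunctions will be reported to Sonex Health by the clinical sites". Section 9.5 lets a site document an AE during the procedure, and section 9.6 has an independent reviewer adjudicate all AEs.

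The document does not mention conversion to another technique or abandonment of an attempt. It defines no attempted-procedure or safety population and no technical-success endpoint.

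**The concern.** Take an eligible, consented subject who is incised for office CTR-US and whose ligament is then released by another technique. On the plain wording of section 7 that subject is not enrolled. If the attempt is stopped without a release, the answer turns on whether the subject received CTR-US, which is undefined. It is also undefined for a simultaneous bilateral case in which one hand is converted.

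The stated objective (section 3) is the safety and effectiveness of office-based CTR-US, and whether single-center results hold up across practices. Attempts that could not be completed bear directly on that question, and device- or procedure-related harm may well appear in them. If they fall outside the denominator, a low related-AE rate can look lower than it is. Every enrolled procedure will also appear completed, because completion is a condition of enrolment. Section 6.2.3 requires screen failures to be logged with the criterion failed; nothing comparable is required for failed attempts.

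**Working it through.** The plan gives no conversion, abandonment or expected AE rate, so there is no figure of its own to reproduce. The check has a textual part and an illustrative part.

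**Text.** Enrolment (section 7), the analysis set (10.2), Day 0 (10.2.1) and the 90-day window (8.2.7) all depend on treatment or receipt of CTR-US. The AE definition (section 9) depends on incision. In the procedural steps of section 7.1, the device is inserted through the incision (step 3) before the ligament is transected (step 7). There is therefore an interval in which AE recording has begun but CTR-US has not been completed. No section says how a subject whose attempt fails in that interval is counted.

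**What the documents say about the rate.** Section 5 describes an office-based study of 88 patients (123 hands) in which all procedures were completed. If that means 0 failures in 88 patients, the Clopper-Pearson upper 95% limit is 1 − 0.025^(1/88) = 4.1%. A rate of a few percent is not excluded.

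**Uncounted attempts.** Let p be the assumed failure rate. Reaching 140 completed subjects (section 10.1) leaves 140p/(1 − p) attempts uncounted. The chance of at least one failure in 140 attempts is 1 − (1 − p)^140.

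| p (assumed) | Uncounted beside 140 | Chance of at least one |
|---|---|---|
| 0.5% | 0.70 | 50% |
| 1% | 1.41 | 76% |
| 2% | 2.86 | 94% |
| 3% | 4.33 | 99% |

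**Effect on the related-AE rate** (Clopper-Pearson 95% intervals, as planned in 10.2.3), with three uncounted attempts and no related AE among 140 completed subjects:

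- As written: 0/140, interval 0 to 2.6%.
- All attempts counted, none with a related AE: 0/143, upper limit 1 − 0.025^(1/143) = 2.5%.
- All attempts counted, each with a related AE (worst case): 3/143 = 2.1%, interval 0.4 to 6.0%.

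With two affected subjects already counted and two uncounted attempts, each with a related AE, 2/140 = 1.4% (0.2 to 5.1%) becomes 4/142 = 2.8% (0.8 to 7.1%).

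**Effect on the primary endpoint.** In the registry in section 5, mean BCTQ-SSS fell from 3.0 to 1.5 at 3 months, a change of 1.5. If three of 143 subjects had no change at all, the mean would shift by 3/143 × 1.5 = 0.03 points. A harsher case adds seven zero-change subjects to the 119 evaluable after 15% attrition (140 × 0.85). The mean is then 1.5 × 119/126 = 1.42, still far from the zero change that the success criterion tests against.

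**The case against.** The best reply is that the sentence was never about conversion. It follows directly on the screening evaluation and reads naturally as covering eligible patients who choose another release, or none, beforehand. Excluding those patients is legitimate. A subject who was incised and instrumented with the device could also be said to have received CTR-US. This stands as an account of likely intent. But the words carry no such limit, and a site or analyst applying them after a conversion would be following the text.

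A reader might infer that harms in failed attempts go unrecorded. The documents do not support that. Section 9 counts AEs from the incision, 9.4 requires device failures to be reported, 9.5 covers AEs during the procedure, 9.6 covers adjudication, and the DSMB in 9.7 reviews AE incidence. Section 10.2 names its set for the primary analyses, and 10.2.3 does not name the AE denominator at all. What is missing is a rule for counting these events; nothing instructs that they be discarded. Sections 7 and 9 can both hold, so this is a gap more than a contradiction.

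The size is also open to challenge. The rate is assumed, the one office-based study described reports every procedure completed, and section 6.1 requires at least 10 prior CTR-US procedures per investigator. The 3/143 example needs every uncounted attempt to carry a related AE. Zero symptom change is pessimistic for a converted subject, whose ligament was still released. All of this stands, and the figures should be read as bounds.

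**Conclusion.** The point holds as a defect of wording with a safety consequence. Followed literally, section 7 un-enrols an attempt converted after incision, and section 10.2 then provides no population for it. For an abandoned attempt the position is unclear because receipt of CTR-US is undefined. Any bias in the reported related-AE rate would be favourable to the device if failed attempts carry more related harm than completed ones. With few events, two or three uncounted subjects could double a low rate, but only on an assumed failure rate of 0.5% to 3% and a worst-case AE pattern. At 0.5% it is about even whether any such attempt occurs.

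A reader might go further and conclude that the plan deliberately removes failures, or that the primary result is at risk. Neither is supported. Conversion is never mentioned, and a shift of about 0.03 points against an expected 1.5 cannot alter a test against zero.

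**What to change.** - **Section 7:** limit the other-method exclusion to decisions made before any incision, and count a subject as enrolled from the first incision for an intended office-based CTR-US. Patients who choose another method beforehand stay unenrolled, as now.
- **Section 10.2:** add an attempted-procedure safety population of all such subjects, and use it as the denominator for device- or procedure-related AEs. Report the number of conversions and abandonments with reasons, including one hand of a bilateral case.
- **Effectiveness:** include these subjects in a sensitivity analysis of BCTQ-SSS change. Placing them in the primary mean is a choice of estimand that this point does not require.
- **Sections 10.2.1 and 8.2.7:** run Day 0 and the 90-day window from the attempted procedure.
- **Section 7.3.2:** reconcile the new enrolment definition with the withdrawal rules, since a subject whose attempt failed may have later surgery, including within the first 3 months.

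The cost is protocol and SAP wording, the existing electronic questionnaires for a few more subjects, and possibly a slightly less favourable AE rate. If no attempt fails, nothing is lost and a claim of complete technical success becomes verifiable.

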7.2 PROCEDURE LOCATION

All CTR-US procedures will be performed in-office. Per the Place of Service Codes set forth by the Centers for Medicare & Medicaid Services (CMS), in-office is defined as a location, other than a hospital, skilled nursing facility (SNF), military treatment facility, community health center, State or local public health clinic, or intermediate care facility (ICF), where the health professional routinely provides health examinations, diagnosis, and treatment of illness or injury on an ambulatory basis ⁴⁰.

7.2.1 Post-treatment Assessments

Postoperative patient care instructions will be standardized among all participating sites to minimize bias. Investigators will instruct subjects to "participate in activities and return to work, as tolerated, based on pain, function, and wound healing status".

7.2.2 Follow-up Assessments

A list of the study assessments performed by the investigational site at each study interval is provided in the table below.

Assessment	Baseline Screening	Procedure	Post- Op	Day 7	Day 14	1 month	3 months	6 months	12 months	24 months
Demographics	\checkmark									
Ultrasound median nerve cross-sectional measurement ¹	4									
CTS-6 ²	√									
Procedure		\checkmark								
Adverse events		\checkmark	\checkmark	V	\checkmark	\checkmark	\checkmark	\checkmark	V	\checkmark

¹Required for all treated hands.

²Measured on both hands

A list of the patient reported outcomes provided by the patient at each study interval is provided in the table below.

Assessment	Baseline Screening	Procedure	Post-Op	Daily 1-14	1 month	3 months	6 months	12 months	24 months
Demographics	1								
Medical history	\checkmark								
BCTQ-SSS ¹	√			√ ²	\checkmark	\checkmark	1	1	\checkmark
BCTQ-FSS	√			√ ²	1	1	1	1	1
MHQ	√			√ ²	1	1	1	1	1
EQ-5D-5L	1			√ ²	1	√	1	1	1
Numeric Pain Scale ¹	√	√	V	√	V	√	√	√	√
Procedure		$\sqrt{1}$							
Return To Activities				√	V	√	1	1	1
Return To Work ³				\checkmark	\checkmark	√			√
Pain Medication	√	√	V	\checkmark	\checkmark	√	√	√	\checkmark

¹Measured on all treated hands.

²Collected only at 14-day evaluation

³Employed subjects only

7.2.3 Unscheduled Follow-up Visits

If subjects are seen for unscheduled visits because of an AE or additional hand surgery, appropriate Case Report Form(s)will be completed, if applicable.

7.2.4 Loss to Follow-up

If a subject fails to comply with follow-up evaluations, the investigational site must make at least two repeated attempts to contact the subject. Each attempt to contact the subject and the method used (e.g., telephone contact, registered letter) must be documented in the subject's records.

7.3 SUBJECT WITHDRAWAL FROM STUDY

7.3.1 Voluntary Withdrawal

A subject may voluntarily withdraw from the study at any time. If a subject officially withdraws from the study, the investigator must ensure that the reason for the withdrawal is documented. If the subject had an AE, the subject should be followed until the resolution of the AE, if possible. Data from these subjects will be included in the analysis up to the point of each subject's withdrawal.

7.3.2 Involuntary Withdrawal

A subject also may be withdrawn by the investigator if the investigator determines that continued subject participation in the study will have a negative effect on the safety of the subject. Data obtained up to the date of subject withdrawal will be included in the study.

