7.3.2.1 Prior to 3 months eVisit following ROBUST Surgery

• Subjects who have any subsequent surgery on either hand during the first 3 months following their procedure will be withdrawn from the study.

7.3.2.2 After 3 months eVisit :

- Subjects Treated with Unilateral CTR-US in ROBUST
 - Surgery in the Contralateral Hand Subjects who have subsequent surgery on the contralateral hand (i.e., non-study hand), including CTR, will not be involuntarily withdrawn from the study. Note that a subsequent CTR-US in the contralateral hand is still not eligible for enrollment in ROBUST.
 - Surgery in the Study Target Hand
 - Subjects who have subsequent surgery on the ROBUST hand that includes the wrist or carpal tunnel region, metacarpals, or thumb (with the exception of trigger thumb release) will be withdrawn from the study.
 - Subjects who have subsequent finger surgery (including trigger finger release) or trigger thumb release that does not affect the wrist or carpal tunnel region will not be withdrawn from the study

• Subjects Treated with Simultaneous Bilateral CTR-US in ROBUST - Subjects who have subsequent surgery on either hand that includes the wrist or carpal tunnel region, metacarpals, or thumb (with the exception of trigger thumb release) will be withdrawn from the study.

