8.2.7 Device- or Procedure-related Adverse Events at 3 Months

Adverse events (AEs) occurring within 90 days of treatment and that are adjudicated as definitely related or probably related to the device, or definitely related or probably related to the

procedure will be included in this endpoint. The incidence of device- or procedure-related AEs within 90 days of treatment will represent a secondary endpoint of the study.

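### For treated subjects, investigator withdrawal under 7.3.2 ends safety follow-up and cuts the data, with no provision for continued AE collection, so later related AEs, upgrades and outcomes can be missed

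*Combined protocol and SAP*

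**What the plan says.** - **Discretionary withdrawal (7.3.2).** "A subject also may be withdrawn by the investigator if the investigator determines that continued subject participation in the study will have a negative effect"; the rest of the sentence makes clear that safety is meant. No time limit is given, and no distinction is made between before and after the procedure. The data rule follows: "Data obtained up to the date of subject withdrawal will be included in the study".
- **Mandatory withdrawal (7.3.2.1 and 7.3.2.2, both under 7.3.2).** Subjects with any further surgery on either "hand during the first 3 months following their procedure will be withdrawn from the study". Section 7.3.2.2 adds surgery-based rules after the 3-month visit. Neither subsection mentions AE follow-up.
- **Voluntary withdrawal (7.3.1).** "If the subject had an AE, the subject should be followed until the resolution of the AE, if possible". The next sentence reads: "Data from these subjects will be included in the analysis up to the point of each subject's withdrawal".
- **Exposure.** Section 7: "Only subjects who receive CTR-US will be considered enrolled in the study". Section 7.3.2.2: "Note that a subsequent CTR-US in the contralateral hand is still not eligible for enrollment in ROBUST". Section 10.2 leaves subjects who withdraw before treatment out of the analysis.
- **Safety outcomes.** Section 8.2.7: "The incidence of device- or procedure-related AEs within 90 days of treatment will represent a secondary endpoint", restricted to AEs adjudicated as definitely or probably related. Section 8.2.9 adds serious related AEs at intervals to 24 months. Section 9.5 asks for resolution date and outcome on the AE form. Section 10.2.3 counts AE incidence per subject, uses exact Clopper-Pearson intervals and rules out imputation.

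**The concern.** In a trial with repeated dosing, a safety withdrawal stops exposure. Here the intervention is over on day 0, and what remains under 7.2.2 is questionnaires and AE assessment. For a treated subject, withdrawal on safety grounds therefore ends only the observation that would show how the safety problem developed. The decision rests with the investigator, and its trigger is a judgement plausibly linked to AE risk. Missing safety data after such a withdrawal cannot be assumed unrelated to the missing events.

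At stake are the completeness of the 90-day related-AE incidence, the serious related-AE outcomes to 24 months, and the recorded outcome of AEs still open at withdrawal. The trial's stated purpose is to determine safety as well as effectiveness.

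**Working it through.** The plan gives no expected AE rate, no safety-withdrawal rate and no AE sample size, so there is no figure of its own to reproduce. The check compares the text and then shows the arithmetic per missed event.

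**Step 1: is any exposure left to stop?** Enrolment requires treatment (Section 7), a later contralateral procedure cannot enter the trial (7.3.2.2), and pre-treatment withdrawals are not analysed (10.2). For every analysed subject the answer is no.

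**Step 2: the withdrawal rules side by side.**

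| | 7.3.1 voluntary | 7.3.2 investigator | 7.3.2.1 and 7.3.2.2 surgery |
|---|---|---|---|
| AE follow-up after withdrawal | Recommended, where feasible | Not mentioned | Not mentioned |
| Data retained | To withdrawal | To withdrawal | Not stated separately; parent section says to withdrawal |

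The AE follow-up sentence is the difference. The data cut is common to 7.3.1 and 7.3.2. No other section extends AE collection past investigator withdrawal.

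**Step 3: which events are lost?** Take a subject withdrawn on day 15 (illustrative).

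- An AE recorded on day 10 and finally classed as definitely or probably related is already counted in 8.2.7. Later events do not change a per-subject incidence. The AE's later seriousness and outcome can still be lost.
- An AE recorded on day 10 but rated only possibly related is not counted. Under 9.3, a probable rating requires other causes to be excluded, and the follow-up that might support this is not provided for.
- A first related AE after day 15 and by day 90 is missed, and no imputation is made.
- Had the withdrawal come after day 90, 8.2.7 would be untouched; only the later outcomes in 8.2.9 and open AE outcomes would be affected.

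**Step 4: size per missed event.** Assume n = 140 (Section 10.1), all kept in the denominator, and m subjects whose first qualifying AE goes unrecorded. The shortfall is m/140. The exact 95% limits for x events are the 2.5% quantile of Beta(x, n − x + 1), with lower limit 0 when x = 0, and the 97.5% quantile of Beta(x + 1, n − x).

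| m missed | Observed if none other recorded | With complete follow-up |
|---|---|---|
| 1 | 0/140 = 0% (0 to 2.60%) | 1/140 = 0.71% (0.02 to 3.92%) |
| 3 | 0/140 = 0% (0 to 2.60%) | 3/140 = 2.14% (0.44 to 6.13%) |
| 5 | 0/140 = 0% (0 to 2.60%) | 5/140 = 3.57% (1.17 to 8.14%) |

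The values of m are assumptions. For a subject with a qualifying AE already recorded, the shortfall is 0.

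**Step 5: does the denominator matter?** It is not stated for subjects withdrawn before day 90. With three other events recorded and m = 3, keeping everyone gives 3/140 = 2.14%, and dropping the three withdrawn subjects gives 3/(140 − 3) = 3/137 = 2.19%. Complete follow-up gives 6/140 = 4.29%. Changing the denominator barely helps; collecting the data does.

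**Step 6: scale.** Section 5 reports one incomplete release among 346 registry patients with complication data, and one case of complex regional pain syndrome among 88 patients in the office-based study. Applied to 140 subjects these give 140 × 1/346 = 0.40 and 140 × 1/88 = 1.59 events. Definitions and follow-up times differ from 8.2.7, so these are only a guide. They suggest that a single missed event could be a large share of the total.

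**The case against.** The strongest reply is that the plan's counting rule already protects the endpoint. Data to the withdrawal date are kept and incidence is per subject, so a subject withdrawn because of a recorded related AE is in the numerator. This stands. A reader might infer that the subjects of greatest safety concern drop out of the 90-day endpoint; the documents do not support that.

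Other parts of the reply also stand:

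- A reader might infer that 7.3.1 imposes a firm duty that 7.3.2 lacks, and that this difference biases the endpoint. The 7.3.1 sentence is only a recommendation where feasible, and 7.3.1 cuts the analysis data at withdrawal too. Copying that sentence into 7.3.2 would not by itself repair 8.2.7.
- A reader might infer that the clause can only end observation. Section 7.3.2 is not limited to treated subjects, and for a consented but untreated subject it can prevent exposure. The point holds for treated subjects only.
- A reader might illustrate the effect as a halving, from 4/140 = 2.9% to 2/140 = 1.4%. That needs two withdrawn subjects with no qualifying AE on record who each then have one. Both the 4 and the 2 would be invented.
- A reader might add that the 3-month BCTQ-SSS loses poor scores. No figure in the documents bears on this.
- If only questionnaires and AE reporting remain, a valid safety trigger for discretionary withdrawal may be rare.

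The safeguards cited in reply do not close the gap. The independent medical reviewer (9.6) has the final say on classification but no stated role in withdrawal, and cannot adjudicate events that are not collected. Board review of AEs (9.7) has the same limit. Section 9.5 asks for resolution and outcome but does not override the data cut. Rarity of the discretionary trigger does not help with 7.3.2.1, where withdrawal is mandatory within the first 3 months. The one registry complication was confirmed at reoperation; its timing is not given, but a reoperation within 3 months would require withdrawal here.

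**Conclusion.** The point holds in a limited form. For treated subjects, withdrawal under 7.3.2 and its subsections ends safety follow-up and cuts the data, with no provision for AE collection afterwards. The possible losses are a first qualifying AE before day 90, a later upgrade in relatedness or seriousness, the outcome of an open AE, and later serious related AEs. Losing an event, an upgrade or an unfavourable outcome makes the safety record look better, and none of these losses adds events.

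The size cannot be derived from the documents. It is 0.71 percentage points per missed first event, assuming 140 subjects all remain in the denominator, and zero where a qualifying AE was already recorded. How many such subjects there will be is unknown. This is a worthwhile low-cost correction to a stated data rule. It does not show that the safety endpoint is invalid.

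**What to change.** 1. In 7.3.2, expressly covering 7.3.2.1 and 7.3.2.2, state that after CTR-US an investigator's withdrawal ends questionnaires but not AE collection. AEs continue to be collected through at least day 90, and ongoing AEs are followed to resolution where possible, unless the subject withdraws consent.
2. Replace the data-cut sentence in 7.3.2 so that AE data obtained after questionnaires stop enter the safety analysis.
3. Align the data cut in 7.3.1 for subjects who leave by choice but agree to AE follow-up.
4. In 10.2.3, state the AE denominator for subjects withdrawn before day 90, and report how many there were and why.

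None of this alters who is withdrawn or any clinical decision; it changes data collection and analysis only. The cost is a few sentences and a follow-up call for a few subjects.
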